If at an Evaluation for Re-treatment visit the subject wants to get re-treated, but the investigator does not agree or vice versa (i.e. the FWS score is not \geq at least 2 by both assessments), the subject will return to the site 4 weeks thereafter for another Evaluation for Re-treatment visit. There is no limit to the number of Evaluation for Re-treatment visits. In order to consider a visit as the End of Cycle visit, there must always be agreement between investigator and subject on a FWS score (at maximum frown) of ≥ 2 .

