7.3 Eligibility Criteria for Re-treatment

The following criteria **MUST** be met for re-treatment:

- At time of re-treatment subject does not have relevant changes to their health status from enrollment, which would have prevented subject's entry into the study according to the inclusion and exclusion criteria.
- The subject must have been randomized to receive treatment and must have received at least one treatment (BoNT/A-DP or placebo).
- A minimum of 12 weeks must have elapsed since the previous study treatment.
- The subject's glabellar lines at maximum frown must have relapsed to a FWS score of 2 or 3 as determined by both the investigator and the subject.
- No relevant infection or inflammation in the planned injection area.
- Negative urine pregnancy test, in women of child-bearing potential.
- The subject must have received fewer than four study treatments.
- The subject must agree and consent to re-treatment.
- Re-treatment will be performed at the latest by week 48.

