4 STUDY ENDPOINTS

4.1 Primary efficacy endpoint(s)

The primary efficacy endpoint is the proportion of subjects among BoNT/A-DP and placebo groups with a FWS score of 0 or 1 and an improvement ≥ 2 points in FWS score (at maximum frown) at the week 4 visit (of the first treatment cycle) relative to baseline (responders), based on both the investigator's and the subject's in-clinic assessments. Thus, the primary endpoint is a composite endpoint comprising investigator and subject assessments of treatment effectiveness.

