4.3 Additional Secondary endpoints

The additional secondary endpoints of this study are:

6. The proportion of responders among BoNT/A-DP and placebo groups with a FWS score of 0 or 1 and an improvement ≥ 2 points in FWS score (at maximum frown) during the first treatment cycle visit relative to baseline, based on both the investigator's and the subject's in-clinic assessments (composite endpoint, at weeks 1, 2 and 8).

Statistical Analysis Plan (SAP)

7. The proportion of subjects with ≥ 2 point reduction in FWS score (at maximum frown) in the BoNT/A-DP and placebo groups during the first treatment cycle visit relative to baseline, based on the independent rater's assessment of photographs (at baseline and visits 2, 4, 12, 16 and 20 weeks after treatment, within the first treatment cycle).
8. Time to onset of effect in the BoNT/A-DP and placebo groups in the first treatment cycle, as measured at weeks 1, 2 and 4 based separately on subject and investigator assessments. Onset of effect defined as at least a 1 point improvement in FWS score from baseline (at maximum frown). In addition, onset of effect will be assessed by subjects daily in the first 2 weeks after treatment, by recordings in the subject diary.
9. The extent of subject perceptions of effect of, and satisfaction with, treatment, in the BoNT/A-DP and placebo groups, during each treatment cycle, as assessed by the FACE-Q Satisfaction with Outcome Scale.
10. The proportion of subjects with a ≥ 1 point reduction in FWS score at rest in the BoNT/A-DP and placebo groups, relative to baseline, during the first treatment cycle, based on the independent rater's assessment of photos.
11. The percentage of subjects with a FWS score of 0 or 1 and an improvement of ≥ 2 points in FWS score at maximum frown (investigator and subject assessment) at four weeks after re-treatment relative to the rating at the preceding end of cycle visit.

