6.6 DRM

For the DRM appropriate listings displaying all relevant data will be provided to the sponsor and serve as a source for the protocol deviations discussion about the classification into major and minor. No unblinding will be done for creation of these listings.

The following protocol deviations will be assessed on a case-by-case basis and a final decision on a possible exclusion from the PP will be done during the DRM:

- Inclusion/exclusion criteria violated
- Use of disallowed medications
- Serious breach of GCP
- Photography not collected or available for all visits
- Site staff performing the study assessment not trained
- Failure to discontinue subjects where appropriate.
- Subject re-treated despite not meeting all re-treatment eligibility criteria

Patients with minor protocol deviations will not be excluded from the PP.

Statistical Analysis Plan (SAP)

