8 STATISTICAL METHODS

8.1 General statistical conventions

All statistical procedures will be completed using SAS version 9.3 or higher.

The statistical analysis of the first treatment cycle and the open label extension phase (cycles 2-4) will be performed after database lock of all data up to the end of the study (can take place in four-weekly intervals from study week 48 until study week 60) and final unblinding.

The statistical testing of the primary endpoint as well as the key secondary endpoints will be one-sided and will be performed using a significance (alpha) level of 0.025. A two-sided McNemar test (using a significance level of 0.05) will be used to compare the response proportions between week 4 re-treatment visit and at the preceding end of the cycle visit. This endpoint will be separately analyzed for each open label extension cycle. Two-sided 95% CIs will be provided when relevant.

Continuous variables will be summarized using descriptive statistics, including number of subjects (n), mean, standard deviation (SD), median, minimum and maximum. One additional decimal point for mean and median and two additional decimal points for SD will be used in addition to the number of decimal points used for the measured values.

For categorical variables, summaries will include counts of subjects and percentages in corresponding categories. Percentages will be rounded to one decimal place.

For statistical analyses “baseline” refers to the last observation before treatment, i.e. pre-treatment values measured on the treatment day (baseline visit, day 0), and if missing or not evaluated, values from screening visit will be used.

All summaries will be presented by treatment group, unless otherwise specified.

Analyses will be performed by visit, irrespective of any time window deviations.

All subject data, including those derived, will be presented in individual subject data listings. Unless otherwise stated, unscheduled visit results will be included in date/time chronological order, within patient listings only. All listings will be sorted by investigational site, patient number, date/time and visit. The treatment group will be stated on each listing. Unless otherwise stated, data listings will be based on the Safety Analysis Set. A listing with demographic data for screening failures will be presented.

Statistical Analysis Plan (SAP)

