8.6.1.1 Multiplicity

The testing of the primary and the five key secondary efficacy endpoints will be performed with appropriate multiplicity control based on the FAS population. The results of each test result will only be considered confirmative if the previous test in the order showed a confirmatory result at a one-sided significance level of 0.025. If the one-sided p-value is larger than 0.025 for any of the tests, the results of the subsequent tests will only be considered exploratory, and not confirmatory. The application of this hierarchical approach keeps the global significance level to 0.025 one-sided and requires no further adjustment of the significance level.

The following order of tests will be applied:

- Primary endpoint (composite endpoint)
- Key secondary endpoint 1 (composite endpoint)
- Key secondary endpoint 2 (composite endpoint)

Statistical Analysis Plan (SAP)

- Key secondary endpoint 3
 - 3.1: The investigator's in-clinic assessments
 - 3.2: The subject's in-clinic assessments
- Key secondary endpoint 4 (composite endpoint)
- Key secondary endpoint 5
 - 5.1: The modified Skindex-16 (GL-QoL) Emotional domain
 - 5.2: The modified Skindex-16 (GL-QoL) Functioning domain
 - 5.3: The modified Skindex-16 (GL-QoL) Overall score
 - 5.4: The FACE-Q Appraisal of Lines Between Eyebrows scale
 - 5.5: The FACE-Q Age Appraisal VAS score

All other analyses (e.g., additional analyses of the primary and the five key secondary efficacy endpoints using other analysis populations or other statistical methods, analyses of additional secondary endpoints) will only be considered exploratory.

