8.6.4 Additional secondary analyses

The additional secondary efficacy endpoints will be analyzed applying the appropriate statistical method for the comparison of both treatment arms. For proportions

- of responders with a FWS score of 0 or 1 and an improvement ≥ 2 points in FWS score at maximum frown,
- of subjects with ≥ 2 point reduction in FWS at maximum frown,
- of subjects with a ≥ 1 point reduction in FWS at rest, and
- of subjects with an improvement of ≥ 2 points in FWS at maximum frown at 4 weeks after re-treatment,

the Cochran-Mantel-Haenszel test (with stratification variable site) and the Pearson χ^2 -test will be applied. In case of a total number of observations below 30, or in case of at least one cell frequency below 5, Fisher's exact test will be used instead of the χ^2 -test. Two-sided 95% CIs for response rates will be calculated, where appropriate. Additionally the cumulative proportions of effects at weeks 1, 2, and 4 will be calculated. Time to onset of effect in the first treatment cycle will be analyzed descriptively and by using the Kaplan-Meier method. Moreover, the daily assessments of the line severity when frowning will be analyzed descriptively. The FACE-Q satisfaction with outcome scale will be analyzed descriptively.

All endpoints, with exception of “responder” 4 weeks after re-treatment, will be analyzed for the first treatment cycle only. The analysis of “responder” 4 weeks after re-treatment will be conducted on observed values only, i.e. subjects with missing investigator or the subject in-clinic assessments on FWS week 4 or at the preceding end of the cycle visit will be excluded from analysis. Subjects who were treated with placebo during the first treatment cycle are excluded from the analysis of this endpoint, but not assigned as being non-responders. A two-sided McNemar test (using a significance level of 0.05) will be used to compare the response proportions between week 4 re-treatment visit and at the preceding end of the cycle visit. This endpoint will be separately analyzed for each open label extension cycle.

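### The exploratory McNemar test of re-treatment response uses a comparator visit at which no eligible subject can be a responder, so 4 to 6 week 4 responders make it significant whatever the number re-treated

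*SAP*

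**What the plan says.** Endpoint 11 (SAP 4.3, Protocol 6.4.2.2) is the percentage of subjects with FWS 0 or 1 and at least 2 points improvement at maximum frown, by investigator and subject, four weeks after re-treatment. Improvement is measured "relative to the rating at the preceding end of cycle visit". In cycle 1, by contrast, response is assessed "at the week 4 visit (of the first treatment cycle) relative to baseline" (SAP 4.1).

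Two rules fix the scores at the visit before re-treatment:

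- Protocol 6.3.2: for a visit to count as End of Cycle, "there must always be agreement between investigator and subject on a FWS score (at maximum frown) of ≥ 2". SAP 3.3 repeats this.
- Protocol 7.3: to be re-treated, the subject's lines "must have relapsed to a FWS score of 2 or 3 as determined by both the investigator and the subject".

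The test is stated in SAP 8.1 ("A two-sided McNemar test (using a significance level of 0.05) will be used to compare the response proportions"), in SAP 8.6.4 and in Protocol 12.4.2. In each place it "will be used to compare the response proportions between week 4 re-treatment visit and at the preceding end of the cycle visit", cycle by cycle. The version (exact, uncorrected or continuity-corrected) is not named.

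SAP 8.6.4 also includes the re-treatment proportion in its list for Cochran-Mantel-Haenszel and Pearson tests, introduced as comparisons of the two arms. It then excludes subjects who had placebo in cycle 1 from this endpoint. It plans 95% CIs for response rates where appropriate. SAP 8.6.1.1 sets the status: "analyses of additional secondary endpoints) will only be considered exploratory".

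**The concern.** A McNemar test is informative when a subject could respond at either of the two paired visits. Here the entry rule for re-treatment fixes the answer at one of them. The null hypothesis of equal proportions then reduces to zero response at week 4, which a handful of responders will reject.

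Efficacy after repeat treatment is part of the stated study purpose (Protocol 5.1). Up to three p-values, for cycles 2, 3 and 4, would be reported next to this endpoint. They could be read as evidence that efficacy holds up on repeat treatment, although the test cannot separate preserved response from response that has largely gone.

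The between-arm tests raise a separate problem: once placebo-first subjects are excluded, there is no second arm to compare.

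**Working it through.** The plan gives no sample size, power or expected discordant count for this test, so there is no figure of its own to reproduce.

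**Step 1. Can an eligible subject be a responder at the End of Cycle visit?** FWS runs from 0 to 3. Day 0 and End of Cycle scores are each 2 or 3 for both raters.

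- Measured from the End of Cycle rating, as endpoint 11 states, the change of that visit from itself is 0.
- Measured from day 0, the largest possible improvement is 3 − 2 = 1 point.
- On either reference the score is 2 or 3, not 0 or 1.

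No permitted combination of scores gives a responder. This also holds for the shorter wording in the SAP 8.6.4 list, which mentions only the 2-point improvement.

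**Step 2. The test with one empty cell.** Let b be the subjects who respond at week 4 but not at End of Cycle, and c the reverse. Then c = 0 and b is the number of week 4 responders.

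- Uncorrected: χ² = (b − c)²/(b + c) = b, on 1 df
- Continuity-corrected: χ² = (|b − c| − 1)²/(b + c) = (b − 1)²/b, on 1 df
- Exact two-sided: p = 2 × 0.5^b

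| b | Uncorrected p | Corrected p | Exact p |
|---|---|---|---|
| 3 | 0.083 | 0.248 | 0.250 |
| 4 | 0.046 | 0.134 | 0.125 |
| 5 | 0.025 | 0.074 | 0.0625 |
| 6 | 0.014 | 0.041 | 0.031 |

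The number re-treated appears in none of the formulas. The threshold is 4 responders (uncorrected) or 6 (corrected or exact).

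**Step 3. What six responders mean as a rate.** The documents do not give the number re-treated per cycle, so N is assumed. The largest value, 525, is the planned BoNT/A-DP arm.

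| Assumed N | 6/N | Wilson 95% CI |
|---|---|---|
| 100 | 6.0% | 2.8–12.5% |
| 200 | 3.0% | 1.4–6.4% |
| 400 | 1.5% | 0.7–3.2% |
| 525 | 1.1% | 0.5–2.5% |

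**Step 4. Chance of a significant exact test when true response is low.** This is P(X ≥ 6) with X ~ Bin(N, π); π is assumed.

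| True response π | N = 100 | N = 200 | N = 400 |
|---|---|---|---|
| 5% | 38% | 94% | >99.9% |
| 10% | 94% | >99.9% | >99.9% |

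At 60% the probability is effectively 1 for N of 100 or more. With 200 or more re-treated, the test would therefore almost always give the same verdict at 10% response as at 60%.

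**Step 5. Subjects re-treated against the rules.** SAP 6.6 foresees the deviation "Subject re-treated despite not meeting all re-treatment eligibility criteria". Such a subject could be a responder at the comparator visit only if both raters scored 0 or 1 and response there were measured from day 0. With one such pair (c = 1):

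- Uncorrected: b = 6 gives 25/7 = 3.57, short of 3.84; b = 7 gives 36/8 = 4.50. The threshold is 7.
- Exact: the threshold is 8 (p = 0.039).

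The conclusion barely changes.

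**The case against.** The strongest reply is that little depends on this test. It is exploratory and outside the hierarchy. SAP 8.6.4 already plans observed-value response rates by cycle, with CIs. No passage says the McNemar test is meant to show preservation of effect, and the low response rates in Step 4 are hypothetical. The planning assumption is 60%, and the earlier Korean glabellar study reported 89.3% by investigator rating at week 4. The stray between-arm listing could be passed over because SAP 8.6.1 applies its tests if appropriate.

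Most of this bears on importance, and it stands to that extent: the impact is limited. It does not make the test informative. If response is as high as expected, the p-value is near zero by construction and adds nothing to the rate.

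Three narrower points also stand:

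- The 60% figure is response measured from day 0, whereas endpoint 11 is measured from the End of Cycle rating. It is a rough yardstick only.
- 525 is a planned arm size, not a strict ceiling, since Protocol 6.3 enrols approximately 700.
- A placebo-randomized subject given active drug in error would remain in the endpoint under the placebo label. A few misallocated subjects do not make a usable comparison arm.

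**Conclusion.** The concern holds. Under the plan's own eligibility rules, the comparator visit contributes no responders. The McNemar p-value is a function of the week 4 responder count alone, with significance at 4 (uncorrected) or 6 (exact or continuity-corrected). This result needs no assumption beyond adherence to the re-treatment criteria. The percentages and probabilities depend on assumed numbers re-treated and assumed response rates.

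The between-arm tests listed for the same endpoint have no second arm once placebo-first subjects are excluded.

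The change should be made, but its reach is small. Only an exploratory analysis is affected. The primary and key secondary conclusions are untouched, and the per-cycle response rates with their CIs remain informative.

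**What to change.** 1. Delete the McNemar test for endpoint 11 from SAP 8.1 and 8.6.4 and from Protocol 12.4.2. If the protocol is not amended, list the departure in SAP Section 9.
2. Remove the re-treatment item from the Cochran-Mantel-Haenszel and Pearson list in SAP 8.6.4.
3. State the analysis outright: week 4 responder proportion in each open-label cycle, BoNT/A-DP-first subjects, observed values, with a Wilson 95% CI. SAP 8.6.2 already names Wilson intervals for the primary endpoint. For this endpoint, this replaces the where-appropriate condition on CIs.

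A comparison with cycle 1 is optional and is not needed to cure the defect. If one is wanted, use the same reference in both cycles: FWS 0 or 1 and at least 2 points improvement from day 0, by both raters. Under the present mixed references, a subject going from 3 to 1 in cycle 1, relapsing to 2 and returning to 1 would count as having lost response at the same week 4 score.

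The day 0 reference has its own cost. That same subject would count as a responder after a 1-point gain from re-treatment. A subject with day 0 score 2, End of Cycle 3 and week 4 score 1 would not count despite a 2-point gain. Endpoint 11 itself should therefore keep its present definition. Report the paired difference with a 95% CI, labelled exploratory, conditional on relapse and re-treatment, and as open-label against blinded ratings.

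The cost is wording in three places, plus a Section 9 entry if the protocol stays as it is. Day 0, End of Cycle and week 4 scores are already collected. The only loss is an exploratory p-value that does not measure how well response is preserved.

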8.7 Safety analyses

This section describes the safety analyses that will be conducted on the double-blind and the open label treatment period, i.e., the safety analyses on all data collected during these treatment periods and all data collected in subjects who dropped-out during one of the treatment periods.

Statistical Analysis Plan (SAP)

All definitions relative to safety endpoints are detailed in the following sections.

Safety analyses will be conducted on the Safety Analysis Set and will be performed for all safety variables specified below.

All safety data will be summarized by treatment group.

The safety analyses of changes from baseline to a specific time point in safety variables (e.g., laboratory parameters, vital signs, and ECG) will only include subjects from the Safety Analysis Set who have data available for both the baseline and the time point under consideration unless otherwise specified.

No statistical testing methods will be applied to statistically evaluate the differences on safety variables between treatment groups. Safety endpoint variables will be analyzed descriptively only.

An additional safety evaluation will be performed for laboratory data, vital signs, and ECG by defining cycle 2 day 0 as baseline for subjects who switched from placebo to BoNT/A-DP.

8.7.1 Treatment Exposure

A summary table displaying the number of subjects by the number of treatment cycles will be prepared. The duration of study drug exposure (calculated as described in section 8.5.1) during each treatment cycle will be analyzed by summary statistics.

8.7.2 Adverse events (secondary safety endpoint 1)

All AEs will be classified by SOC and PT according to MedDRA Version 19.0 or higher.

In summaries by SOC and PT, adverse events will be sorted by decreasing frequency within each SOC and PT. In summaries by PT, AEs will be sorted by decreasing frequency within each PT.

AE summary tables will be presented for TEAEs and AESIs separately by treatment cycle and will include the number and percentage of subjects with any:

- TEAE/AESI
- TEAE/AESI related to study medication (AE will be defined as related if causality is definitely, probably or possibly or if causality assessment is missing)
- TEAE/AESI related to injection procedure (AE will be defined as related if causality is definitely, probably or possibly or if causality assessment is missing)
- Severe TEAE/AESI

Statistical Analysis Plan (SAP)

- Severe TEAE/AESI related to study medication
- Severe TEAE/AESI related to injection procedure
- TEAE/AESI leading to discontinuation
- Study drug related TEAE/AESI leading to discontinuation
- Serious TEAE/AESI
- TEAE/AESI leading to death.

All TEAEs as well as all AESIs will be summarized by SOC, PT and treatment group using frequency counts and percentages (i.e. number and percentage of subjects with an event).

The number of events, as well as the number and rate of affected subjects will be reported by SOC and PT for all TEAEs and for all AESIs separately.

Adverse events will be separated to pre-treatment AEs and TEAEs. TEAEs are defined as all AEs with onset or worsening (increase in severity) after receiving first dose of study medication (independent of whether it is BoNT/A-DP or placebo). If it cannot be determined whether an AE is treatment-emergent due to a partial onset date, then it will be counted as such.

TEAEs and AESIs will be analyzed overall (for BoNT/A-DP or placebo), and for BoNT/A-DP treatment group additionally separately per first treatment cycle or open label extension phase: events starting on or after first treatment up to before open label extension (first cycle), and events starting on or after re-treatment until end of study (open label phase). If it cannot be determined whether an AE started during the first treatment cycle or the open label extension phase due to a partial onset date, then it will be counted as having started during first treatment cycle. The assignment of AEs to the different cycles of the open label extension phase will be done similarly: AEs will be assigned to a certain cycle if they start on or after treatment of the respective cycle but before treatment of the next cycle. In case that there is no subsequent treatment cycle, all AEs (starting on or after the last treatment) until end of study will be assigned to the last cycle.

Events of subjects who started the first treatment with placebo but then entered the open label extension for re-treatment with BoNT/A-DP will be considered to placebo for the first cycle and to BoNT/A-DP for the open label phase.

TEAEs and AESIs (per SOC and PT) will also be summarized by seriousness, severity, relationship to study medication, and relationship to procedure using frequency counts and percentages (i.e. number and percentage of subjects with an event).

Statistical Analysis Plan (SAP)

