8.3.6 Description of Treatment

The subject will receive five injections (4U per 0.1 mL injection) per treatment visit (total dose of 20 U, 0.5 mL) at a minimum interval of 12 weeks, for a maximum of four treatments during the study. Subjects randomized to receive placebo will receive placebo for their first treatment and may enter the open label extension after the first treatment cycle and receive BoNT/A-DP for the subsequent treatments. The treatment schedule is illustrated in Section 2.2.

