3.1 General study design

This multicenter Phase 3 study is comprised of two parts. The first part of the study is a randomized, double blind, placebo-controlled, phase which aims to demonstrate efficacy and safety of BoNT/A-DP compared with placebo. The second part is an open label extension phase to evaluate efficacy after repeat treatments and long term safety.

Subjects can receive a maximum of four treatment cycles over the duration of the study, a single treatment in the first cycle compared with placebo, and up to three subsequent treatments in the open label extension study.

Adult subjects less or equal 75 years old with moderate to severe glabellar frown lines at maximum frown with an important psychological impact as indicated by scores >0 on either the Emotional or Functioning subscales of the modified Skindex-16 (GL-QoL) will be enrolled in this study. Approximately 18 sites (50% in EU and 50% in US) will enroll in total 700 evaluable subjects. Applying a 10% drop out rate will result in a total number of completing subjects of about 630.

The overall study scheme is presented below:

[figure not shown]

The duration of study participation for each subject will be up to 14 calendar days of screening followed by 48 to 60 weeks of treatment (re-screening will not be permitted). The first treatment cycle will be a double blinded cycle followed by up to three open label treatment cycles. Each cycle will be at least 12 weeks and can be prolonged in 4-week increments, depending on treatment effect. Re-treatment is possible until study-week 48.

[figure not shown]
Statistical Analysis Plan (SAP)

Visit Scheme/Treatment Cycle 1 (double blind)

Visit Scheme/Treatment Cycles 2, 3, 4 (open label)

Statistical Analysis Plan (SAP)

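### Open-label adverse event tables by study cycle pool subjects who are one BoNT/A-DP exposure apart, and no table by exposure number is planned

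*SAP*

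**What the plan says.** SAP 8.7.2 sets the unit of the adverse event overview: "AE summary tables will be presented for TEAEs and AESIs separately by treatment cycle and will include" a list of subject counts. For the open-label phase it adds that "AEs will be assigned to a certain cycle if they start on or after treatment of the respective cycle but before treatment of the next" one. For subjects who began on placebo, events "will be considered to placebo for the first cycle and to BoNT/A-DP for the open label phase".

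The first cycle counts as a cycle whichever product was given. SAP 3.1 says: "Subjects can receive a maximum of four treatment cycles over the duration of the study, a single treatment in the first cycle compared with placebo". Protocol 8.3.6 says: "Subjects randomized to receive placebo will receive placebo for their first treatment and may enter the open label extension after the first treatment cycle", with BoNT/A-DP from then on.

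SAP 8.7.1 uses the same unit for treatment counts: "A summary table displaying the number of subjects by the number of treatment cycles will be prepared".

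The plan does recognise that switchers need a new starting point, but only for other safety data. SAP 8.7 says: "An additional safety evaluation will be performed for laboratory data, vital signs, and ECG by defining cycle 2 day 0 as baseline" for subjects who moved from placebo to BoNT/A-DP. Protocol 12.4.2 places the same rule under safety endpoint 3. Adverse events are safety endpoint 1 and have no counterpart.

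**The concern.** A study cycle is not the same thing as a BoNT/A-DP exposure number. The two agree for subjects who began on active and differ by one for those who began on placebo. Since SAP 8.7.2 merges both groups into one BoNT/A-DP group after cycle 1, a cycle 2 rate is neither a first-exposure nor a second-exposure rate.

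The trial is meant to supply long-term safety data over multiple treatment cycles and a safety database for approval (SAP 2.2, objective 3). A natural reading of tables for cycles 1 to 4 is how event rates move with repeated BoNT/A-DP treatment, particularly for the events of special interest, which concern spread of toxin effect. On the planned layout, a real change in risk between one exposure and the next would be blurred in every open-label column, and the reader could not tell by how much.

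**Working it through.** **Inputs.** Planned allocation 3:1, 525 BoNT/A-DP and 175 placebo, 10% drop-out leaving about 630 (SAP 5). At most four cycles, the first placebo-controlled (SAP 3.1). Attribution and cycle assignment as in SAP 8.7.2.

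**Plan's own figures.** 700 × 0.75 = 525 and 700 × 0.25 = 175; 700 × 0.9 = 630, which splits into 472.5 and 157.5. These reproduce. No stated sample size, alpha or power is in question.

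**Step 1: exposure number by cycle.**

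| Study cycle | Active-first subjects | Placebo-first subjects | BoNT/A-DP column |
|---|---|---|---|
| 1 | exposure 1 | none (placebo) | not mixed |
| 2 | exposure 2 | exposure 1 | mixed |
| 3 | exposure 3 | exposure 2 | mixed |
| 4 | exposure 4 | exposure 3 | mixed |

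**Step 2: share of a column that is one exposure behind.** Let rA and rP be the proportions of the active-first and placebo-first arms that reach the cycle. The share is s = 175·rP / (525·rA + 175·rP). The documents give neither rA nor rP, so the unequal cases are assumptions:

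- rA = rP: s = 175/700 = 25% (also 157.5/630).
- rA = 1.0, rP = 0.5: s = 87.5/612.5 = 14%.
- rA = 0.7, rP = 1.0: s = 175/542.5 = 32%.
- rA = 0.5, rP = 1.0: s = 175/437.5 = 40%.

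Shares above 25% are plausible in later cycles. Re-treatment requires relapse to a score of 2 or 3 by both raters (Protocol 7.3), which placebo-first subjects may meet sooner in cycle 1 than subjects whose treatment is still working.

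**Step 3: effect on a column rate.** The column for cycle k shows (1 − s)·p(k) + s·p(k−1), where p(j) is the risk at exposure j. If p(k) = p(k−1), nothing is distorted. Two illustrations, both with assumed risks at the later exposure:

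- 10% at exposure k−1 and 5% at exposure k: 0.75 × 5% + 0.25 × 10% = 6.25% at s = 25%; 0.60 × 5% + 0.40 × 10% = 7.0% at s = 40%.
- Eyelid ptosis at 4.5% on first exposure (6 of 134 in the earlier Korean glabellar-line study, Protocol 4.4.2.1) and an assumed 2.0% on repeat: 0.75 × 2.0% + 0.25 × 4.5% = 2.6% at s = 25%. Across s = 14% to 40% the result runs from about 2.4% to 3.0%.

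**Step 4: treatment counts.** A placebo-first subject with four cycles has had three BoNT/A-DP treatments. If the SAP 8.7.1 table is not split by arm and progression is equal, the number with four cycles is 700/525 = 1.33 times the number with four BoNT/A-DP treatments. If the table is split by arm, the reader can subtract one cycle in the placebo arm and nothing is overstated.

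**The case against.** The strongest reply has five parts.

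- **Safety data are shown by treatment group.** SAP 8.7 says so generally, and SAP 8.5.1 summarizes exposure by treatment group with the double-blind and open-label phases apart. This stands for exposure: a reader might infer that the plan overstates repeat exposure, but that follows only if the 8.7.1 table ignores the arm split. It does not rescue the adverse event tables, because SAP 8.7.2 moves placebo-first subjects into BoNT/A-DP after cycle 1.
- **Nobody is lost.** A reader might infer that first exposures in placebo-first subjects drop out of the database and weaken the bound on rare events. The documents do not support that. SAP 8.7.2 also calls for an overall analysis, in which their open-label events count under BoNT/A-DP, so everyone ever exposed is covered.
- **Objective 3 speaks of cycles, not dose numbers.** True. The by-cycle tables answer the objective as worded and should stay.
- **Regrouping creates its own mixture.** This also stands. Exposure 1 would combine blinded cycle 1 data with open-label cycle 2 data. In cycle 1, weeks 2 and 8 are clinic visits, with a full physical examination at week 2; in cycle 2 both are telephone calls (Protocol Table 9-1). It argues against replacing the by-cycle tables, not against adding to them.
- **The effect may be small.** In the ptosis example the shift is about 0.6 percentage points, or 4 subjects in 630, inside a 95% interval of roughly 1.4% to 3.9% around 2.6%. Subject listings (SAP 8.1) would also allow the view to be rebuilt by hand.

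Table templates are in a separate document (SAP 1). A split could appear there, but neither the protocol nor the SAP asks for one.

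**Conclusion.** The point holds as a gap in presentation. The BoNT/A-DP columns for cycles 2, 3 and 4 each combine subjects one exposure apart: 25% of the column under equal progression, about 14% to 40% under the assumed unequal progression. No adverse event table specified in either document separates them, and the switcher re-alignment stops at laboratory data, vital signs and ECG.

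Whether any rate is distorted depends on risk varying with exposure number. The documents do not establish this, and the repeat-exposure risks used above are assumed. Safety is analysed descriptively, so no test or error rate changes, and the randomized cycle 1 comparison of BoNT/A-DP with placebo is unaffected. It is a worthwhile, inexpensive improvement to how repeat-treatment safety is reported, not a flaw in the trial's main conclusions.

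**What to change.** Keep the by-cycle tables and the first-cycle versus open-label split. Then:

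- **SAP 8.7.2:** derive a BoNT/A-DP exposure number from 1 to 4, with cycle 2 of placebo-first subjects set to exposure 1, cycle 3 to exposure 2 and cycle 4 to exposure 3. Add TEAE and AESI summaries by this number, with placebo in cycle 1 as its own column.
- **SAP 8.7.2:** split the open-label columns by first-cycle treatment, so that blinded and open-label first exposures stay distinguishable. Footnote that exposure 1 combines data collected under different blinding and visit schedules.
- **SAP 8.7.1:** count subjects by number of BoNT/A-DP treatments received, separately from the placebo cycle.

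The cost is one derived variable from data already collected, a few extra tables and a footnote. Trial conduct does not change. The wording should be settled before database lock and unblinding, the point by which Protocol 12.5 has the SAP finalized.
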